Excluded criteria	(1) Neonatal data with unclear clinical basic information ; (2) Lack of traceability core information data ; (3) data that the test results cannot be analyzed and interpreted ; (4) Sample collection is not qualified and unwilling to cooperate with re-sampling. (5) Newborns with severe deformity and severe lethal inherited metabolic diseases
Grouping and sample size	A total of 2000 neonates were included, including 500 cases of non-significant hyperbilirubinemia (TSB / TCB $<$ 205umol / L) ; (2) 500 cases of significant hyperbilirubinemia (205umol / L \leq TSB / TCB $<$ 342umol / L) ; (3) 500 cases of severe hyperbilirubinemia (TSB / TCB \geq 342umol / L) ; 4 Extremely severe hyperbilirubinemia 500 cases (TSB / TCB \geq 428umol / L).
data collection	(1) Basic information : gender, gestational age, date of birth, birth weight, height, head circumference, mode of conception, Apgar score and parents ' information ; (2) Perinatal information : parity, parity, mode of delivery, fetal

	
membranes, amniotic fluid, placenta, umbilical cord, intrauterine distress, group B streptococcal infection, pregnancy complications such as gestational hypertension, diabetes, etc.
 
(3) Jaundice information : blood types of parents and newborns, feeding methods, monitoring jaundice values, jaundice treatment methods and related test results ;
 
(4) Test results : Collect genetic analysis results, notes, etc.

Statistical processing	IBM-SPSS 26.0 statistical software was used to analyze the test results. Logistic multivariate regression analysis was used to evaluate the correlation between genotype and clinical phenotype, and mediating variables were used to analyze the correlation between gene-gene interaction and genotype-phenotype.
abbreviation	neonatal hyperbilirubinemia, NHB; total serum bilirubin, TSB; transcutaneous bilirubin, TCB; Principal Investigator, PI.

1. Research background

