significant hyperbilirubinemia ($TSB / TCB < 205\text{umol} / \text{L}$), 500 cases of significant hyperbilirubinemia ($205\text{umol} / \text{L} \leq TSB / TCB < 342\text{umol/L}$), 500 cases of severe hyperbilirubinemia ($TSB/TCB \geq 342\text{umol/L}$) and 500 cases of extremely severe hyperbilirubinemia ($TSB/TCB \geq 428\text{umol} / \text{L}$).

4. Inclusion criteria

- (1) Informed consent of parents or guardians ;
- (2) Age : 1-28 days, gestational age ≥ 35 weeks ;
- (3) Birth weight ≥ 2.5 kg and < 4 kg.

5. Excluded criteria

- (1) Neonatal data with unclear clinical basic information ;
- (2) Lack of traceability core information data ;
- (3) data that the test results cannot be analyzed and interpreted ;
- (4) Sample collection is not qualified and unwilling to cooperate with re-sampling.
- (5) Newborns with severe deformity and severe lethal inherited metabolic diseases

6. termination criteria

- (1) The family members of the newborn included in the study requested termination at any time ;
- (2) The relevant management departments require termination.

7. outcome index

Through the comprehensive analysis of genetic variation information and jaundice clinical data, the carrying rate of pathogenic genes of common hereditary jaundice diseases in newborns was counted, and the difference of carrying rate of pathogenic genes in different degrees of jaundice was understood. To explore whether there is a difference in the degree of jaundice carrying multiple and single jaundice pathogenic genes, and to analyze the correlation between gene polymorphism and clinical manifestations (phenotypic polymorphism) of neonatal hyperbilirubinemia.

8. Grouping and sample size

This study is a prospective observational study. According to the positive mutation rate of NHB-related genes in neonatal hyperbilirubinemia, P is about 30 %, the test level α

= 0.05 and the allowable error $\delta = 2 \%$, n (sample size) = ($U\alpha / \delta$) $2 * p * (1 - P) \approx$ 2000 cases. A total of 2000 neonates were included, including 500 cases of non-significant hyperbilirubinemia ($TSB / TCB < 205\text{umol} / L$) ; (2) 500 cases of significant hyperbilirubinemia ($205\text{umol} / L \leq TSB / TCB < 342\text{umol} / L$) ; (3) 500 cases of severe hyperbilirubinemia ($TSB / TCB \geq 342\text{umol} / L$) ; (4) Extremely severe hyperbilirubinemia 500 cases ($TSB / TCB \geq 428\text{umol} / L$) .

9. Recruiting

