This study will recruit subjects in the outpatient and inpatient departments of pediatrics, neonatology, and obstetrics in the South China Neonatal Genetic Screening Alliance (including cooperation units of 49 hospitals).

10. Clinical evaluation index

- (1) The carrying rate, positive rate, negative rate and high-frequency mutation sites of common NHB-related gene mutation sites in neonates ;
- (2) The difference in the carrying rate of NHB-related pathogenic genes in neonates with different degrees of jaundice ;
- (3) The difference of jaundice degree between carrying multiple and single jaundice pathogenic genes ;
- (4) Gene-gene interaction and genotype-phenotype correlation.

11. Methods

11.1 gene sequencing

A total of 24 genes were included in 29 NHB-related genetic diseases, including bilirubin metabolic disorders, congenital bile acid synthesis or transport disorders, red blood cell metabolic defects, lipid metabolic abnormalities, and metal metabolic abnormalities. The detected genes included ABCB11, ABCB4, ABCC2, ABCD3, ACOX2, AKR1D1, AMACR, ATP7B, ATP8B1, CYP7B1, G6PD, GBA, HBB, HSD3B7, JAG1, NOTCH2, NPC1, NPC2, NR1H4, SLC10A1, SLC25A13, SMPD1, TJP2 and UGT1A1. Gene and genetic disease related information refer to OMIM and Orphanet database.

Target gene sequence capture and library construction. Three drops of heel peripheral

blood were collected by filter paper, and genomic DNA was extracted by magnetic bead method. The target gene sequence was captured by multiplex PCR amplification method, covering all exon regions and adjacent intron regions ($\pm 50\text{bp}$) of the target gene. A total of 900 amplicons were designed for 24 genes and completed in two amplification systems. The target sequence library was obtained after amplification-purification-re-amplification-re-purification. The library was quantified using a Qubit[®] 3.0 fluorescence quantitative instrument (Thermo Fisher Scientific), and the library length was determined using an Aglient 2100 biological analyzer (Agilent) (228-378 bp).

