11.2 Information and data collection

Researchers should truthfully fill in the test results of the subjects and other relevant information, and ensure that the information is true and reliable. The specific

information and data to be collected are as follows :

(1) Sign informed consent ;

(2) Jaundice gene detection : Take out the special filter paper blood collection card, disinfect with alcohol and dry the heel blood collection site, collect heel peripheral blood, drop three drops on the filter paper.

(3) Detection of jaundice value by percutaneous jaundice meter : The family members of the subjects rented the percutaneous jaundice meter for free under the guidance of the doctor, and used the ' single measurement mode ' to measure the forehead, chest and inner thigh of the subjects every day for a total of 2 weeks.

(4) Collect demographic characteristics : screening number, name, gender, gestational age, date of birth, birth weight, body length, head circumference, mode of conception, Apgar score and parental information ;

(5) Perinatal information : parity, parity, mode of delivery, fetal membranes, amniotic fluid, placenta, umbilical cord, intrauterine distress, group B streptococcal infection, pregnancy complications such as gestational hypertension, diabetes, etc.

(6) Jaundice information : parents and newborns blood type, hemolysis three tests, feeding methods, percutaneous jaundice value, jaundice treatment and related test results ;

(7) Gene detection results : Collect gene analysis results, notes, etc.

12. Statistical processing

IBM-SPSS 26.0 statistical software and R language (Version 4.1.0) were used for statistical analysis of the test results. The carrying rate of common NHB-related gene mutation sites in neonates was counted, and the differences in the carrying rate of NHB-related pathogenic genes in neonates with different degrees of jaundice were compared. To explore the difference in the degree of jaundice carrying multiple and single jaundice-related genes. The measurement data were expressed as mean \pm standard deviation ($x \pm s$), and the t test was used for comparison between groups. The count data were expressed as values or rates (%), and the chi-square test was used for comparison between groups. Unconditional logistic multivariate regression analysis

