was used to evaluate the correlation between genotype and clinical phenotype, and mediating variables were used to analyze the correlation between gene-gene interaction and genotype-phenotype.

13. data monitoring

(1) Case Report Form The case report form (CRF) was used in this study. The researcher ensures the authenticity, accuracy and integrity of the data in the original case of each enrolled (signed informed consent) newborn. The researcher or authorized researcher confirms and fills in the original medical record and submits it to the researcher / clinical coordinator. The data points in the original medical record are entered into the case report form system by the researcher / clinical coordinator.

(2) Data audit and locking After all data-related queries have been resolved, the main researchers, data managers, and statistical analysts will confirm the statistical analysis of the population, lock the database, and sign the audit report at the same time. The locked data must not be changed.

(3) Data privacy regulations All members of the research team, including lead researchers and their authorized researchers, must comply with all local and regional regulatory requirements and applicable privacy regulations (such as the ' Health Insurance Carriage and Liability Act ').

Each newborn participating in this study will be assigned a unique number and an institutional identifier.

All research data will be stored in a confidential electronic system and stored for at least 3 years after the completion of the study.

The coding table for recording neonatal information and research will be kept by the researcher (PI) in a locked file cabinet or in a password-protected database. Only researchers and their authorized researchers have the right to access the coding table.

The coding table that records the name of the hospital and the institution identification number will be saved by the research team in a locked file cabinet, which is only limited to access by limited research members.

The identity of each subject of observation should be kept confidential in research

reports and related publications.

14. adverse reactions

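### Section 12 has no provision for genes with few carriers: if they are entered singly, ordinary logistic regression can give infinite odds ratios and uninformative Wald tests for index 4

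*Combined protocol and SAP*

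**What the plan says.** Section 12 assigns the genotype-phenotype question to "Unconditional logistic multivariate regression analysis", which "was used to evaluate the correlation between genotype and clinical phenotype". The Abstract's statistical entry says the same: "Logistic multivariate regression analysis was used to evaluate the correlation between genotype and clinical phenotype". Neither place mentions penalised or exact fitting, zero cells, a minimum carrier count or pooling. Neither says which test supplies the p-value, how severity is coded, or whether each gene is its own term. Gene-gene interaction is to be handled through mediating variables that are not specified further.

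The panel is wide: "A total of 24 genes were included in 29 NHB-related genetic diseases" (section 11.1). The groups are fixed in section 8: "A total of 2000 neonates were included, including 500 cases of non-significant hyperbilirubinemia", with 500 in each of the other three classes. The only carriage figure is in section 8, about 30% positive over all genes together in hyperbilirubinemic newborns. No rate is given for any single gene; section 12 says only that "The carrying rate of common NHB-related gene mutation sites in neonates was counted".

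Unadjusted comparisons of carrier rates between groups (section 10, index 2) are assigned separately to chi-square.

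**The concern.** Unconditional logistic regression is fitted by ordinary maximum likelihood. When all carriers of a gene fall on one side of the outcome, the likelihood keeps rising as the coefficient grows, so no finite estimate exists. Software stops at an arbitrary large coefficient with a very large standard error, and the Wald p-value comes out close to 1.

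This failure has a direction. A gene carried by several extremely severe infants and by no comparator infant is strong evidence of a link with severity, yet a Wald-based table would list it as non-significant, or the analyst might drop it. Index 4 is where this matters, because it is the analysis that would supply adjusted genotype-phenotype estimates. Without a rule fixed beforehand, dropping or pooling genes would be decided after the results are seen.

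**Working it through.** **Inputs from the protocol.** 24 genes (section 11.1); 4 × 500 = 2000 infants, overall positive rate about 30%, α = 0.05, allowable error 2 percentage points (section 8).

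**Assumptions.** Per-gene carriage and its contrast between classes are not in the protocol and are varied below. Tests are two-sided at 5%.

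**1. The plan's own figure.** (1.96/0.02)² × 0.30 × 0.70 = 2017, which agrees with the stated 2000. This is a precision calculation for one overall proportion and does not address single genes.

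**2. What 30% implies per gene.** Spread evenly and independently, −ln(0.70)/24 = 1.49% per gene. If two genes supplied 50%, 70% or 80% of this, the other 22 would average −ln(0.70) × (1 − share)/22 = 0.81%, 0.49% or 0.32%.

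**3. What a zero cell does.**
- 10 carriers of 500 versus 0 of 500: an ordinary fit stops at log-odds 15.2, SE 633, Wald p = 0.98. The stopping values depend on the software's convergence rule.
- 10 versus 0 in a 1000 versus 1000 split: R's glm gives log-odds 14.6, SE 279, Wald p = 0.96.
- Other methods on 10/500 versus 0/500: Firth odds ratio (10.5/0.5)/(490.5/500.5) = 21.4, penalised likelihood-ratio p = 0.0008; chi-square p = 0.0015; Fisher p = 0.0019; ordinary likelihood-ratio p = 0.0002.

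**4. How often a zero occurs.** With the same carriage p in every class, one class of 500 is empty with probability q = (1 − p)^500. At least one of four is empty with probability 1 − (1 − q)^4. A comparator half of 1000 is empty with probability (1 − p)^1000.

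| p | one class of 500 empty | any of four empty | half of 1000 empty |
|---|---|---|---|
| 1.5% | 0.05% | 0.2% | <0.001% |
| 0.8% | 1.8% | 7.0% | 0.03% |
| 0.5% | 8.2% | 29% | 0.7% |
| 0.2% | 37% | 84% | 13.5% |

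**5. Power at an assumed 2.0% versus 0.2%**, by exact enumeration of two binomials of 500, with Wald counted as non-rejecting when a cell is zero: Wald 42%, Fisher 75%, Firth 83%, chi-square 84%, ordinary likelihood ratio 89%. The comparator class is empty in 0.998^500 = 37% of datasets. With 1000 versus 1000, Wald reaches 85%.

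**6. Rejection rate with no true difference** (500 versus 500, nominal 5%):

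| carriage | Firth | chi-square | ordinary likelihood ratio |
|---|---|---|---|
| 0.2% | 0.3% | 1.4% | 5.9% |
| 0.5% | 2.4% | 4.6% | 9.4% |
| 1.0% | 4.0% | 4.3% | 7.0% |

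**7. Gene-gene terms.** If interactions are fitted as logistic terms, then under independence two genes at 1.5% give 0.015² × 2000 = 0.45 expected double carriers in the whole study. A 15% gene paired with a 1.5% gene gives 0.15 × 0.015 × 2000 = 4.5, and at least one class has none in 79% of datasets. Here sparsity does not need skewed gene frequencies.

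**The case against.** The other side has four good arguments.

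- **The planned chi-square already finds such genes.** For index 2 this is correct. Chi-square has 84% power in the scenario above and no inflation under the null at the rates checked. A reader might infer that index 2 is distorted too; section 12 does not support that, because it assigns group comparisons of counts to chi-square. But chi-square gives no covariate-adjusted estimate, so it does not settle index 4.
- **A p-value near 1 is a Wald result, and the plan names no test.** This is also correct. The likelihood-ratio test from the same fit detects the 10 versus 0 gene. It is not a full rescue: it rejects a true null 9.4% of the time at 0.5% carriage, and the odds ratio is still infinite.
- **No per-gene rate is given.** A reader might infer that rare genes make up most of the panel. The protocol does not say so. The 30% figure averages 1.5% per gene, where empty classes are negligible, and section 11.1 also brings variants of unclear significance into the result statistics, which would raise counts if they were modelled.
- **The plan does not say that genes enter singly or that two classes of 500 are contrasted.** This stands. With a binary or ordinal outcome one empty class need not cause divergence, so 29% and 84% are chances of an empty class, not failure rates of the stated model.

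**Conclusion.** The point holds as a conditional weakness of index 4. Section 12 names only ordinary logistic regression and has no rule for separation. If sparse genes or gene-gene terms are entered singly, some odds ratios can be infinite and their Wald tests uninformative, and the genes most specific to severe disease are the ones exposed.

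The size depends on unstated inputs. For single genes the problem is negligible near 1.5% carriage, material at about 0.5% when classes of 500 are contrasted, and common at 0.2%. A 1000 versus 1000 split largely removes it at 0.5% and leaves about a 13.5% chance of an empty comparator half at 0.2%. The loss from 83% (Firth) to 42% (Wald) rests on the assumed 2.0% versus 0.2% contrast, 500 per group, and Wald reporting. It would be too strong to say that the model fails for most of the panel, or that index 2 is compromised.

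**What to change.** In section 12, and in the matching Abstract entry:

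- Fit gene-level and gene-gene logistic models by Firth penalised likelihood, with profile-likelihood confidence intervals and penalised likelihood-ratio tests, in R, which section 12 already names.
- State the outcome coding and which genes or terms enter singly.
- Pre-specify a minimum carrier count below which genes are pooled by the disease classes listed in section 11.1.
- Keep chi-square for the unadjusted carriage comparisons. A general switch to Fisher is not needed and would lower power from 84% to 75% in the scenario above.

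The cost is SAP wording and one R package, with no new data. The downside is small: penalised odds ratios are slightly shrunk, and the test is conservative for very rare genes (0.3% rejection under the null at 0.2% carriage).

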This study is a prospective observational study. Three drops of heel peripheral blood samples were collected from 2000 newborns, and 24 genes of 29 NHB-related genetic diseases were analyzed. All dry blood spot samples that met the inclusion criteria could be included in the genetic analysis. At the same time, the clinical data of these 2000 newborns were collected, and the daily jaundice monitoring at home was performed using the percutaneous jaundice meter (YSJ-20). The data were synchronized to the mobile phone jaundice follow-up doctor assistant small program for storage statistics. The family members can view the jaundice risk level and obtain free doctor consultation in the small program.

The purpose of this study is to study the carrying rate of pathogenic genes of common hereditary jaundice diseases in newborns, to understand whether there is a difference in the carrying rate of pathogenic genes in different degrees of jaundice, to explore whether there is a difference in the degree of jaundice carrying multiple and single jaundice pathogenic genes, and to analyze the correlation between gene polymorphism and clinical manifestations (phenotypic polymorphism) of neonatal hyperbilirubinemia, so as to evaluate the feasibility of jaundice gene screening program in the detection of jaundice-related genetic metabolic diseases.

Based on the 'Classification Criteria and Guidelines for Genetic Variation (2017)', the variation pathogenicity of genetic testing is divided into five categories : known pathogenic, possible pathogenic, unclear significance, possible benign and benign. In this study, known pathogenic and possible pathogenic are classified as positive results. The pathogenicity of the mutation site is mainly based on the pathogenic mutation database and the latest literature reports.

The classification criteria of jaundice were based on the American Academy of Pediatrics (AAP) 2022 edition of neonatal hyperbilirubinemia management guidelines for gestational age ≥ 35 weeks and the latest version of 2023 guidelines to interpret the management of neonatal hyperbilirubinemia-the diagnosis and intervention criteria of neonatal hyperbilirubinemia in the American Academy of Pediatrics and multi-national clinical management guidelines. The 2000 neonates were divided into 500 cases of non-

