High-throughput sequencing and bioinformatics analysis. The library was diluted, added sequencing primers, and sequenced on the Illumina NextSeq 550 platform (PE150). The effective sequencing data were aligned to the human reference genome (Human _ B37) by BWA (Burrows-Wheeler Aligner) software. GATK (Genome Analysis ToolKit) was used to analyze the variation information, and ANNOVAR software was used to annotate the variation, including the annotation information of dbSNP database, Thousand Human Genome Project and other existing databases. The annotation content covers population frequency, mutation type, function prediction (SIFT, Polyphen2, Mutation Taster, etc.), HGMD, Clinvar and other pathogenic classification information. Based on the ' Classification Criteria and Guidelines for Genetic Variation (2017) ', the pathogenic interpretation of genetic variation was divided into five categories : ' pathogenic ', ' possible pathogenic ', ' unclear significance ', ' possible benign ' and ' benign '. Among them, ' pathogenic ', ' possible pathogenic ' and ' unclear significance ' were included in the statistics of test results.

Validation of positive loci. For children with autosomal recessive double heterozygosity and children with autosomal dominant single heterozygosity, Sanger sequencing was used to verify the loci of their parents.

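### Gene-gene interaction, part of evaluation index 4, is assigned to a mediation method that does not test it, and no other stated analysis does

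*Combined protocol and SAP*

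**What the plan says.** Section 10, item 4, lists "Gene-gene interaction and genotype-phenotype correlation". Item 3 is a separate index: "The difference of jaundice degree between carrying multiple and single jaundice pathogenic genes".

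Section 12 gives three pieces of analysis that bear on these:

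- For index 3: "To explore the difference in the degree of jaundice carrying multiple and single jaundice-related genes". The tests named are a t test for measurements and a chi-square test for counts.
- For genotype against phenotype: "Unconditional logistic multivariate regression analysis", which "was used to evaluate the correlation between genotype and clinical phenotype". No covariates, outcome coding or product term are stated.
- For gene-gene interaction: "mediating variables were used to analyze the correlation between gene-gene interaction and genotype-phenotype". The abstract's row on statistical processing says the same. No exposure, mediator, outcome, gene pair or interaction scale is named in either place.

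Two statements bear on who counts as a carrier. In section 3, "known pathogenic and possible pathogenic are classified as positive results". Section 11.1 adds variants of unclear significance to those two classes, and all three "were included in the statistics of test results".

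**The concern.** Interaction asks whether the effect of one gene depends on the presence of another. Mediation asks how much of an effect passes through an intermediate variable. Both genotypes are fixed at conception and neither lies on a causal path from the other, so a mediation model with genes as its variables does not estimate interaction.

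The logistic regression covers the genotype-phenotype half of index 4. The interaction half then has no method that addresses it, and the nearest available result is multiple versus single. That comparison is valid for index 3. The risk is that a significant result there is reported as evidence that genes act together, when two separate effects could have produced it.

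**Working it through.** **The plan's own figure.** Section 8 uses n = (U/δ)² × P × (1 − P), with P = 30%, α = 0.05 and δ = 2%. Two-sided: (1.96/0.02)² × 0.30 × 0.70 = 9604 × 0.21 = 2016.8, which agrees with the stated 2000 or so. This is the precision of one overall rate and says nothing about interaction.

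**Algebra.** Take two independent genes, each multiplying the odds of severe jaundice by g, with no interaction. Single carriers have odds ratio g and double carriers g², both against non-carriers.

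- Multiple versus single: g²/g = g.
- Product term: g²/(g × g) = 1.

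So index 3 shows an odds ratio of 2 when g = 2, although there is no interaction on the odds-ratio scale.

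**Assumed inputs.** The documents give no carriage rate or odds ratio per gene. I assumed 1000 infants at or above 342 umol/L and 1000 below (the four quotas of 500, pooled in pairs), two equally common genes, and either gene carried by 30% of the upper group. Tests are at 5%: Pearson chi-square for multiple versus single, and Wald for the product term in the saturated two-gene logistic model.

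**Hand check at g = 2** (9.0% source carriage per gene). Expected counts:

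| | ≥342 | <342 |
|---|---|---|
| Double carriers | 26.4 | 7.8 |
| Single carriers | 273.6 | 162.2 |

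- Odds ratio: (26.4/7.8)/(273.6/162.2) = 2.0.
- Chi-square: 470 × (26.4 × 162.2 − 7.8 × 273.6)² / (300 × 170 × 34.2 × 435.8) = 2.85.
- Approximate rejection rate: P(Z > 1.96 − √2.85) = P(Z > 0.27), or 39%.

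**Simulation, no interaction (100,000 replicates, zero cells counted as not rejected):**

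| OR per gene | Source carriage, each gene | Multiple vs single rejects | Product term rejects |
|---|---|---|---|
| 1.5 | 11.6% | 20.8% | 4.6% |
| 2 | 9.0% | 38.7% | 4.1% |
| 3 | 6.3% | 54.3% | 2.9% |

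At OR 2 with source carriage of 10%/5% and 5%/5%, multiple versus single rejects in 25% and 12%, and the product term in 3% of each.

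**The scale matters.** If the effects truly add, the joint odds ratio is 2g − 1. Multiple versus single is then (2g − 1)/g and the product term (2g − 1)/g².

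- g = 2: 3/2 = 1.5 and 3/4 = 0.75.
- g = 3: 5/3 = 1.67 and 5/9 = 0.56.

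At the same source carriage, multiple versus single rejects in about 14% and 11%, and the product term in about 10% and 18%. The product term is therefore specific only for departure from multiplicative odds ratios.

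**Power under pure synergy** (joint OR 3, no single-gene effect):

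| Source carriage | Multiple vs single | Product term |
|---|---|---|
| 15%/5% | 76% | 62% |
| 10%/5% | 58% | 46% |
| 5%/5% | 33% | 15% |

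For an interaction OR of 2 on top of OR 2 per gene, at 8.5%/8.5%, product-term power is about 30%.

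**Multiplicity.** 24 × 23/2 = 276 pairs. If all were estimable and null, 276 × 0.05 = 13.8 would be expected below 0.05 with no control.

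**The case against.** The strongest reply is that this is a wording problem. 'Mediating' may be a translation of 'moderating', and the logistic regression named in the same sentence can hold a product term. That is plausible, and it means the documents do not prove that a mediation analysis will be run. The word would still be wrong in two places and the term still unstated, with 276 pairs to choose from.

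A second reply is that interaction carries little weight here. It is absent from the objectives (section 2), the stated purpose (section 3), the outcome index (section 7) and the analysis schedule (section 18). It appears only in index 4 and the method sentence. That stands, and it limits the severity.

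Third, the simulation is not the planned test. The plan assigns no cut at 342 to any analysis, and index 3 might use a t test on bilirubin or all four groups. The percentages therefore illustrate the problem and do not predict this study's results; the algebra applies to odds ratios at any single cut. Likewise, the 30% in section 8 refers to neonatal hyperbilirubinemia in general. Placing it in infants at or above 342 is my assumption, and carriage there could be higher.

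Fourth, the product term has less power than multiple versus single under pure synergy. That is true. Its advantage is specificity on one scale.

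**Conclusion.** The point holds: index 4 includes gene-gene interaction, the stated method does not test it, and no other stated analysis isolates it. Under the assumptions above, multiple versus single rejects in about 21% to 54% of studies when there is no multiplicative interaction, against 3 to 5% for a product term.

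Four stronger readings are tempting, and the documents do not support them.

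- A reader might infer that a significant multiple-versus-single result is to be expected whether or not genes interact. In these two-gene runs at up to 30% carriage, it occurs in 12% to 54%, mostly under half.
- A reader might infer that the product term separates synergy from effects that add. It tests departure from multiplication, and it rejects more than 5% of the time when effects are additive.
- A reader might take G6PD with UGT1A1 as the hypothesis that motivates the study. Section 1 cites the pair as an example of earlier work confined to one or two genes.
- A reader might assume the data are in hand and unanalysed. Section 11.2 describes data still to be collected and section 18 schedules analysis for April to June 2024; neither shows the current state.

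Severity is modest: an exploratory index, with a specific and cheap correction.

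**What to change.** In section 12 and the abstract, replace the mediation wording for gene-gene interaction with text to this effect:

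> Gene-gene interaction will be tested by a gene A × gene B product term in the logistic regression, with both main effects included. The term tests departure from multiplicative odds ratios. The interaction odds ratio with 95% confidence interval will be reported, with the odds ratios for A only, B only and both, each against neither.

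The three odds ratios let readers judge the additive scale as well. Then:

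- State the outcome coding and covariates of that logistic model, which section 12 leaves open.
- Name in advance the pair or pairs to be tested. UGT1A1 × G6PD, cited in section 1, is a natural candidate. Treat the remaining pairs as exploratory, with false discovery rate control.
- Fix one carrier definition for this model, saying whether variants of unclear significance count.
- Report multiple versus single as carrier burden, not as an interaction test.
- If a mediation analysis is also intended, describe it separately and name a non-genetic mediator.

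**Cost.** A short text change in two places, a carrier definition and a multiplicity rule; no new data items. If analysis has already begun, label the change post hoc. Power is low for uncommon pairs, about 46% at 10%/5% and 15% at 5%/5% in the pure-synergy case, so the plan should say that a null result does not show absence of interaction.
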